## 13.2 Synthesis

Most of the studies previously completed were conducted using losmapimod oral tablets given with food. All subjects in these previous studies were adult males or females and included healthy volunteers or subjects with atherosclerosis, hypercholesterolemia, coronary artery disease, myocardial infarction, rheumatoid arthritis, COPD, major depressive disorder, neuropathic pain, or focal segmental glomerulosclerosis. Single oral doses as high as 60 mg and

repeated oral doses as high as 15 mg BID for up to 24 weeks were well-tolerated. One study in COPD reported dosing at 15 mg BID for up to a year (Pascoe et al., 2017). Most AEs observed were related to exacerbation of disease; others were typically reported by a similar proportion of subjects on losmapimod and placebo. Losmapimod did not consistently result in more study drug-related SAEs or deaths than placebo. There was no clinically relevant difference in laboratory measures, ECGs, or vital signs with losmapimod versus placebo. No adverse events that can definitely be attributed to losmapimod have been identified.

Based on the observed efficacy for inhibiting or reducing aberrant DUX4 expression and therefore activity in FSHD cells, the PD and safety data from nonclinical studies, and the extensive clinical safety data available in the public domain from over 3,500 dosed subjects, the benefit/risk balance supports clinical development with losmapimod in FSHD.

## **15. APPENDIX: DRUGS POTENTIALLY AFFECTING MUSCLE FUNCTION**

List of drug(s) or supplements that potentially may affect muscle function includes, but is not limited to:

1. Statins
2. Steroids
3. Testosterone or other growth hormone agonists
4. Beta-agonists
5. Creatine
6. Colchicine
7. Benzylpenicillin

## DOCUMENT REVISION HISTORY

VERSION	DATE	AUTHOR/ UPDATED BY	COMMENTS
V1.0	11-MAR-2020	NA	NA
V1.1	20-JUL-2020	[REDACTED]	
1. Added three exploratory endpoints in section 1.2.3:
 

3. Skeletal muscle tissue replacement by fat using whole-body MRI

• Lean Muscle Volume (LMV)

• Muscle Fat Fraction (MFF)

• Muscle Fat Infiltration (MFI)

 
2. Added some endpoints in section 4.1 IA#2 analysis, see below:
 

• Summary tables of classic TUG and FSHD-optimized TUG.

• PK Summaries

• Summary table of muscle strength by quantitative dynamometry

• Summary table of distance of walking measured by 6-MWT

• Summary table of reachable work space (RWS)

• Summary table lung ventilator function as measured by Spirometry

• Summary table of physical function by MFM

• Summary table of FSHD-HI total score

• Summary table patient global impression of change

• Summary table of FSHD-RODS total score

 
Updated “Lean Muscle Mass” to “Lean Muscle Volume” in section 4.1 IA#2 analysis
 
3. Added more details for derivation of composite MRI endpoints in Appendix 6

			
4. Added muscle PK parameters of losmapimod in section 1.2.2 and section 3.3
 
5. <del>Added “ratio to baseline” analysis for pHSP27/total HSP27</del>
 
6. Added missing data handling rule for missing DUX4 composite score in section 2.3.5
 
7. Deleted the summary of “the reasons for screen failure” in section 3.1.1
 
8. Deleted “number of years the subject had the disease” and “duration of time from diagnosis to the start of losmapimod” and updated “number of D4Z4 repeats” to “number of FSHD repeats” in section 3.1.3

V1.2	13-AUG-2020	[REDACTED]	
1. Added “median imputation” in section 2.3.5 for “DUX4 COMPOSITE SCORE”

V2.0	25-SEP-2020	[REDACTED]	
1. Removed muscle PK parameters of losmapimod in section 1.2.2 and section 3.3 in order to align with protocol version 3.
 
2. Removed muscle fat fraction (MFF) and muscle fat infiltration (MFI) parameters in section 1.2.3 in order to align with protocol version 3.
 
3. Updated appendix 4 to add 6th gene for the subset and steps for determining the top 2 transcripts.

V2.1	17-MAR-2021	[REDACTED]	
1. Added open-label extension objectives and endpoints to align with protocol version 5.
 
2. Updated figure 1 in order to align with protocol version 5.
 
3. Added visit windows in table 1 to capture additional visits specified in protocol version 5.
 
4. Added muscle PK parameters of losmapimod in section 1.3.2 and section 3.3 in order to align with protocol version 5.
 
5. Updated dynamometry section 3.4.8 and added appendices 7, 8, 9, and 10 to clarify analysis.
 
6. Added manual muscle testing section 3.4.9 to align with protocol version 5.
 
7. Updated reachable work space section 3.4.4 to clarify descriptive statistics.
 
8. Updated MedDRA version to version 23.0
 
9. Added sensitivity analysis section 3.6.

V2.2	26-MAR-2021	[REDACTED]	
1. Updated secondary endpoint description in section 1.3.2.
 
2. Updated visit windows in table 1.
 
3. Clarified dynamometry analysis in section 3.4.8.

V2.3	23APR2021	[REDACTED]	
1. Added study extension disposition details to section 3.1.1.
 
2. Added additional demographics detail to section 3.1.3.

			
 
3. Add treatment compliance definition to section 3.1.6.
 
4. Added exposure detail to section 3.2.1.
 
5. Added clarifying text for cohorts in section 3.3.
 
6. Updated dynamometry normalization calculation in section 3.4.8.
 
7. Changed MMT statistics from change from baseline to change from first observation.
 

V2.4	30APR2021	[REDACTED]	
 
1. Removed 'optimized' from FSHD TUG.
 
2. Updated treatment compliance section 3.1.6 to clarify dose for main study.
 
3. Exclusion details added to MRI section 3.4.2.
 
4. Text added to dynamometry section 3.4.8 to clarify presentation of dominant vs non-dominant.
 
5. Text added to summary of major changes section 5 for presentation of FSHD-RODS and FSHD-HI data.
 

V3.0	10JUN2021	[REDACTED]	
 
1. Clarified protocol deviation section 3.1.2 by adding 'significant' to description.
 
2. Text added to summary of major changes section 5 for presentation of MRI data.
 
3. Clarified in section 3.4.8 that both normalized and raw hand-held data will be analyzed.
 
4. Removed item 5 (ratio to baseline) from document revision history for version 1.1
 
5. Added correlation analyses to section 3.4.2
 
6. Added details about visit observation calculation to section 3.4.2
 

V4.0	20OCT2021	[REDACTED]	
 
1. Updated SAP adjusted protocol windows to reflect error with EOS visit day
 
2. Add (Q1+Q2+Q3+Q4) to section 3.4.4.
 
3. Add percent change from baseline to manual dynamometry in section 3.4.8.
 
4. Appendix added for MMT mapping rules
 
5. Add MMT individual muscles to section 3.4.9.
 

V4.1	30SEP2022	[REDACTED]	
 
1. Removed study assessments for extension: MRI, discovery biomarkers, RWS, TUG, muscle ultrasound, MMT, MFM, dynamometry, FSHD-RODS, FSHD-HI, PGIC, 6-MWT, and spirometry
 
2. Updated study objectives and endpoints for the extension to reflect removed study assessments
 
3. Removed language specifying that the 15 mg dose of study drug is administered as two 7.5 mg tablets
 
4. Updated analysis windows for new extension visit schedule
 

V6.0	07DEC2023		
 
1. Updated analysis window in section 2.3.5 by adding week 216, 228, 240, 252, 264, and 276
 

## ABBREVIATIONS

Abbreviation	Term
AE	Adverse Event
C max	Maximum observed plasma concentration
CRF	Case Report Form
CSR	Clinical Study Report
DUX4	Double homeobox 4
ECG	Electrocardiogram
EOS	End of study
EOT	End of treatment
FEV 1	Forced expiratory volume in 1 second
FSHD	Facioscapulohumeral muscular dystrophy
FSHD-HI	Facioscapulohumeral muscular dystrophy – Health Index
FSHD-RODS	FSHD Rasch-built Overall Disability Scale
FVC	Forced vital capacity
HSP27	Heat Shock Protein 27
MedDRA	Medical Dictionary for Regulatory Activities
MFM	Motor Function Measure
MMT	Manual muscle testing
MRI	Magnetic resonance imaging
PD	Pharmacodynamic(s)
PGIC	Patient Global Impression of Change
pHSP27	Phosphorylated HSP27
PK	Pharmacokinetic(s)
PT	Preferred
qPCR	Quantitative polymerase chain reaction
QTcF	QT interval by Fredericia
RWS	Reachable Work Space
SAE	Serious Adverse Event
SAP	Statistical Analysis Plan
SOC	System Organ Class
SI	Système International
SE	Standard error
TEAE	Treatment-emergent Adverse Event
T max	Time to reach maximum observed plasma concentration
TUG	Timed Up and Go
QMT	Quantitative myometry testing

## 1 INTRODUCTION

The purpose of this statistical analysis plan (SAP) is to describe the procedures and the statistical methods that will be used to analyze, and report results for Protocol FIS-001-2019.

### 1.1 MAIN STUDY OBJECTIVES

#### 1.1.1 Primary Objective

The primary objective of this study is to evaluate the safety and tolerability of long-term dosing of losmapimod tablets in subjects with facioscapulohumeral muscular dystrophy 1 (FSHD1).

#### 1.1.2 Secondary Objectives

The secondary objectives of the study are:

1. To assess target engagement of losmapimod tablets in blood and skeletal muscle over long-term dosing
2. To evaluate repeated dose pharmacokinetics (PK) of losmapimod tablets in subjects with FSHD1 over long-term dosing

#### 1.1.3 Exploratory Objectives

Exploratory objectives of the study are:

1. To evaluate on-treatment change in target engagement and DUX4 activity and other disease transcripts in skeletal muscle needle biopsy
2. To evaluate on-treatment change in skeletal muscle by [REDACTED]
3. To evaluate on-treatment change in skeletal muscle function by clinical outcome assessments
4. To evaluate on-treatment change in upper and lower limb mobility in the outpatient setting
5. To evaluate on-treatment change in lung ventilatory function
6. To evaluate on-treatment change in circulating proteins associated with DUX4 expression or muscle injury or repair

## 1.2 EXTENSION OBJECTIVE

### 1.2.1 Primary Objective

To evaluate the safety and tolerability of long-term dosing of losmapimod tablets in subjects with FSHD1

## 1.3 MAIN STUDY ENDPOINTS

### 1.3.1 Primary Endpoint(s)

The primary endpoint is the assessment of safety and tolerability based on adverse events (AEs), serious adverse events (SAEs), clinically significant laboratory test results, electrocardiograms (ECGs) and vital signs (safety endpoints)

### 1.3.2 Secondary Endpoint(s) / Pharmacodynamic

Secondary endpoints are as follows:

1. Changes from baseline in pHSP27, total HSP27, and in the ratio of pHSP27/total HSP27 as measured by sorbitol stimulated peripheral whole blood (pharmacodynamic [PD] endpoint).
2. Changes from baseline in pHSP27, total HSP27, and in the ratio of pHSP27/total HSP27 in muscle during the dosing period (pharmacodynamics [PD] endpoint).
3. Plasma and muscle concentrations of losmapimod (pharmacokinetic [PK] endpoint)

### 1.3.3 Exploratory Endpoint(s)

Changes from baseline during the dosing period in the following:

1. DUX4 activity and disease specific gene transcripts by quantitative polymerase chain reaction (qPCR) of skeletal muscle using a subset of DUX4-regulated and other disease specific gene transcripts
2. Skeletal muscle lean tissue volume by whole-body magnetic resonance imaging (MRI)
3. Skeletal muscle tissue replacement by fat using whole-body MRI
4. Correlations between MRI composite measures of classic TUG, FSHD TUG, and RWS and traditional measures of classic TUG, FSHD TUG, and RWS
5. Skeletal muscle echogenicity by ultrasound (selected muscles)
6. Reachable Work Space (RWS) with and without weights

7. Ambulatory function by classic and FSHD TUG
8. Physical function by Motor Function Measure (MFM) domain 1
9. Muscle strength by quantitative manual dynamometry
10. Disease impact by subject report using FSHD-Rasch-built Overall Disability Scale (FSHD-RODS)
11. Disease impact by subject report using FSHD-Health Index (FSHD-HI)
12. Disease impact by subject report using Patient Global Impression of Change (PGIC)
13. Upper and lower limb mobility in the outpatient setting using wearables
14. Change in ambulation as measured by the 6-minute walking test (6-MWT)
15. Change in lung ventilatory function as measured by Spirometry

## 1.4 EXTENSION ENDPOINT

### 1.4.1 Primary Endpoint

The primary endpoint is the safety and tolerability based on AEs, clinical laboratory test results, ECGs, and vital signs.

## 1.5 SUMMARY OF THE STUDY DESIGN

[figure not shown]
### 1.5.1 General Study Design and Plan

This is a single-center, open-label pilot study that will investigate the safety, tolerability, PK and target engagement during long-term dosing with losmapimod tablets in adult subjects with FSHD1. Subjects will be evaluated during an 8-week pre-treatment period (baseline) and will be treated with losmapimod for approximately 1 year and assessed at regular intervals for change from the baseline assessment.

During the extension, subjects will attend clinic visits approximately every 24 weeks and have a safety phone call 12 weeks between in-person clinic visits until study drug approval or until study termination. The extension of this study will enable continued investigation of the safety and tolerability during long-term dosing with losmapimod tablets in adult subjects with FSHD1.

The study design is depicted in Figure 1 below:

**Figure 1** Study Design Schema

6-MWT=6-minute walking test; D=day; COAs=clinical outcome assessments; DUX4=double homeobox 4; FSHD-HI=facioscapulohumeral muscular dystrophy-Health Index; FSHD-RODS=FSHD-Rasch-built Overall Disability Scale; MFM=Motor Function Measure; MRI=magnetic resonance imaging; PGIC=Patients' Global Impression of Change; PK=pharmacokinetics; PRO=patient-reported outcome; QMT=quantitative myometry; RWS=Reachable Workspace; TUG=Timed Up and Go; W=week. Only subjects terminating the study after Week 60 will have the Visit 10 End of Study visit. Subjects proceeding to the extension will continue to Week 72 visit. Note: All visits during the extension will have a  $\pm$  4-week window; early termination visits can occur at any time.

### 1.5.2 Sample Size and Statistical Power Considerations

Sixteen subjects are planned to be treated with losmapimod. While this sample size is not based on statistical considerations, a sample size of 16 subjects receiving losmapimod is considered sufficient to obtain estimates of the safety, tolerability, PK, and target engagement properties of losmapimod tablets over long-term dosing and to inform initial assumptions on the potential impact of treatment on biomarkers and clinical outcome assessments compared to the pre-treatment period.

## 2 STATISTICAL CONSIDERATIONS

### 2.1 GENERAL CONSIDERATIONS

All descriptive statistics for continuous variables will be reported using mean, standard deviation (SD), median, minimum, and maximum. Standard error (SE) will be reported for all change from baseline tables. Categorical variables will be summarized as number of subjects and their percentages.

### 2.2 DEFINITIONS OF ANALYSIS SETS

There is only one analysis set for the study, i.e. safety analysis set, which is defined as subjects who received at least one dose of losmapimod.

## 2.3 DEFINITIONS AND CONVENTIONS FOR DATA HANDLING

### 2.3.1 Baseline Definition

Baseline: Baseline value is defined as last observed measurement occurring prior to the study drug.

### 2.3.2 Study Day

Study Day will be calculated from the reference start date and will be used to show start/stop day of assessments and events. Reference start date (Day 1) is defined as the first day of treatment. Study Day = date of event – reference start date + 1. In the situation where the event date is partial or missing, Study Day, and any corresponding durations will appear partial or missing in the listings.

### 2.3.3 End of Treatment

End of treatment: The definition of end of treatment is the last non-missing visit post-baseline that the subject is on treatment.

### 2.3.4 End of Study

End of study: The definition of end of study is the subjects' last completed visit.

### 2.3.5 Analysis Visit Windows

The following non-overlapping visit windows will be used to assign data to visits for data analyses:

Table 1 Visit windows for measurements

Adjusted Defined Windows Visit	Scheduled Study Day	Maximum Windows
Baseline Visit (First dose/Day 1)	Day 1	<= Day 1
Week 4 post-treatment	Day 28	>Day 1 to <=Day 42
Week 8 post-treatment	Day 56	>Day 42 to <=Day 98
Week 20 post-treatment	Day 140	>Day 98 to <=Day 182
Week 32 post-treatment	Day 224	>Day 182 to <=Day 266
Week 44 post-treatment	Day 308	>Day 266 to <=Day 350
Week 56 post-treatment	Day 392	>Day 350 to <=Day 406
60 Weeks post-treatment (EOS, Protocol Visit 10)	Day 420	>Day 406
64 Weeks post-treatment (Protocol Week 72)	Day 448	>Day 406 to <=490

Adjusted Defined Windows Visit	Scheduled Study Day	Maximum Windows
76 Weeks post-treatment (Protocol Week 84)	Day 532	>Day 490 to <=Day 574
88 Weeks post-treatment (Protocol Week 96)	Day 616	>Day 574 to <=Day 658
100 Weeks post-treatment (Protocol Week 108)	Day 700	>Day 658 to <=Day 742
112 Weeks post-treatment (Protocol Week 120)	Day 784	>Day 742 to <=Day 826
124 Weeks post-treatment (Protocol Week 132)	Day 868	>Day 826 to <=Day 952
148 Weeks post-treatment (Protocol Week 156)	Day 1036	>Day 952 to <=Day 1120
172 Weeks post-treatment (Protocol Week 180)	Day 1204	>Day 1120 to <=Day 1288
196 Weeks post-treatment (Protocol Week 204)	Day 1372	>Day 1288 to <=Day 1456
220 Weeks post-treatment (Protocol Week 228)	Day 1540	>Day 1456 to <=Day 1624
244 Weeks post-treatment (Protocol Week 252)	Day 1708	>Day 1624 to <=Day 1792
268 Weeks post-treatment (Protocol Week 276)	Day 1876	>Day 1792 to <=Day 1960

Only subjects terminating the study after Week 56 post-treatment will have the Week 60 follow-up (EOS) visit. Subjects proceeding to the extension will continue to 64 Weeks post-treatment (protocol week 72) visit. Subjects will remain in the extension until 90 days after commercial drug is available post regulatory approval or until the study is discontinued by the sponsor. During the extension, subjects will attend clinic visits approximately every 24 weeks. All subjects who complete or discontinue from treatment will complete a safety follow-up visit 7 days ( $\pm 3$  days) after the last dose of study drug.

If multiple visits are recorded in the same analysis window, the later visit will be used in the analysis.

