### 3.1.3 Treatment and Observation Period

In the pre-treatment period, subjects will visit the study site 3 times, at Baseline (Visit 2, Day 1), Visit 3 (Week 4  $\pm$  1 week), and Visit 4 (Week 8  $\pm$  1 week). In the on-treatment period, the

second muscle biopsy will occur at Visit 5 (Week 14 ± 2 weeks); then subjects will visit the study site every 12 weeks from Visit 5 (Week 14 ± 2 weeks) until Visit 10 (Week 64 ± 2 weeks [end of study]). Assessments are described in Table 2.

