### **3.1.5 Treatment Duration**

The total duration for this study will be approximately 68 weeks, and the total treatment duration will be approximately 52 weeks in the main portion of the study. Subjects will have the option of participating in the extension portion of the study until 90 days after commercial drug is available post regulatory approval or study termination.

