**Table 2 Schedule of Assessments – Main Study**

Assessment	Pre-Treatment Period				Treatment Period						Follow-up Period	
	Study Visit a											
	Visit 1 (Screening [Day -28 to -1]) b	Visit 2 (Baseline [Day 1])	Visit 3 (Week 4 [±1 wk])	Visit 4 (Week 8 c [±1 wk])	Visit 5 (Week 14 [±2 wks])	Visit 6 (Week 24 [±2 wks])	Visit 7 (Week 36 [±2 wks])	Visit 8 (Week 48 [±2 wks])	ET Visit	Visit 9 d (Week 60/ [±4 wks] EOT or Rollover to Extension)		
Informed consent	X											
Eligibility	X											
Reconfirm eligibility				X								
Demographics	X											
Medical history	X											
FSHD History e	X											
Outpatient visits	X	X	X	X	X	X	X	X	X	X		
Weight/Height f	X								X		X	
Physical examinations g	X											
Vital signs h	X	X	X	X	X	X	X	X	X	X	X	
ECG i	X			X	X	X	X	X	X	X	X	
Genetic Confirmation of FSHD1 j	X											
Blood sample for serology testing k	X											
Urine drug screen	X											
Serum hCG test l	X											
Urine hCG test l				X	X	X	X	X	X	X		

Assessment	Pre-Treatment Period				Treatment Period					Follow-up Period
	Study Visit a									
	Visit 1 (Screening [Day -28 to -1]) b	Visit 2 (Baseline [Day 1])	Visit 3 (Week 4 [±1 wk])	Visit 4 (Week 8 c [±1 wk])	Visit 5 (Week 14 [±2 wks])	Visit 6 (Week 24 [±2 wks])	Visit 7 (Week 36 [±2 wks])	Visit 8 (Week 48 [±2 wks])	ET Visit	Visit 9 d (Week 60/ [±4 wks] EOT or Rollover to Extension)
Serum FSH (postmenopausal females only)	X									
Serum chemistry	X			X	X	X	X	X	X	X
Haematology	X			X	X	X	X	X	X	X
Coagulation studies	X									
PK (blood) m				X	X	X	X	X	X	
PD (blood) n				X	X	X	X	X	X	
MRI o	X						X		X	X
Muscle US		X			X	X	X		X	X
Skeletal muscle needle biopsy				X p	X p					
Discovery biomarkers (serum)				X	X			X		
PD/Target engagement (Muscle)				X	X					X
Losmapimod concentration (muscle)				X	X					X
RWS	X		X	X	X	X	X	X	X	
TUG r	X		X	X	X	X	X	X	X	

Assessment	Pre-Treatment Period				Treatment Period					Follow-up Period							
	Study Visit a																

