	Visit 1 (Screening [Day -28 to -1]) b	Visit 2 (Baseline [Day 1])	Visit 3 (Week 4 [±1 wk])	Visit 4 (Week 8 c [±1 wk])	Visit 5 (Week 14 [±2 wks])	Visit 6 (Week 24 [±2 wks])	Visit 7 (Week 36 [±2 wks])	Visit 8 (Week 48 [±2 wks])	ET Visit	Visit 9 d (Week 60/ [±4 wks] EOT or Rollover to Extension)							
Muscle strength by quantitative dynamometry with hand-held device	X		X		X	X		X	X	X							
Muscle strength by quantitative dynamometry with bed frame equipment	X		X							X							
MFM domain 1	X			X		X		X	X	X							
FSHD-RODS	X		X			X			X	X							
FSHD-HI	X		X			X			X	X							
PGIC					X	X	X	X	X	X							
6-MWT	X		X	X	X	X	X	X	X	X							
Spirometry		X				X		X	X	X							
Losmapimod dispensing				Study Drug will be dispensed starting at Visit 4. Resupply will be provided as needed throughout the study, until EOT													
Outpatient Mobility Assessment		Intermittently from Visit 2 to End of Study															
AE Monitoring		Continuous from signing of ICF to End of Study															
Medications review		Continuous from signing of ICF to End of Study															

a. Unscheduled visits can be scheduled at the discretion of the principal investigator to perform any assessments related to any AEs/SAEs that arise.

b. Subjects are required to fast for at least 4 hours prior to the screening visit.

c. Visit 4 is the end of the pre-treatment period and the beginning of the treatment period. Dosing will begin at Visit 4.

d. Any visit can be split into 2 days with overnight hotel stay as needed to accommodate performance of MRI and US, or to accommodate busy site schedules.

- e. Specific questions about FSHD history will be included in the baseline medical history exam.
- f. Height will be measured at screening only
- g. A full physical examination, including a neurological examination, will be performed at Screening. Symptom-directed physical examinations and laboratory assessments can be performed at any time at the discretion of the investigator.
- h. Vital sign measurements will be performed after subjects have rested for at least 5 minutes.
- i. Standard 12-lead ECGs will be performed after the subject has been supine for at least 5 minutes. ECGs will be collected at screening, before dosing only at Visit 4, and at approximately 3 hours ( $\pm$  90 minutes) after dosing for all other on-treatment visits.

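### SAP Table 1 dates main-study Visits 6 to 10 four weeks too late after first dose, so an early Visit 9 is filed under Week 44 and Visit 10 lands in the Visit 9 window

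*SAP*

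**What the plan says.** SAP section 2.3.2 fixes the time origin: "Reference start date (Day 1) is defined as the first day of treatment". Protocol Table 2, footnote c, says when that is: "Visit 4 is the end of the pre-treatment period and the beginning of the treatment period. Dosing will begin at Visit 4". Visit 4 is at protocol Week 8 ± 1 week.

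Protocol Table 2 puts Visits 6, 7 and 8 at Weeks 24, 36 and 48 (each ± 2 weeks) and heads the Visit 9 column "Week 60/ [±4 wks] EOT or Rollover to Extension". Protocol section 3.1.3 has visits "every 12 weeks from Visit 5 (Week 14 ± 2 weeks) until Visit 10 (Week 64 ± 2 weeks [end of study"]. Protocol section 3.1.5 adds that "the total treatment duration will be approximately 52 weeks in the main portion of the study".

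SAP section 2.3.5 states that the Table 1 windows assign data to visits. After the Week 4 and Week 8 rows, the main-study rows are Weeks 20, 32, 44, 56 and 60 post-treatment, with upper limits at Days 182, 266, 350 and 406; the last row, "60 Weeks post-treatment (EOS, Protocol Visit 10"), takes everything after Day 406. The first extension row is "64 Weeks post-treatment (Protocol Week 72"). The tie rule reads: "If multiple visits are recorded in the same analysis window, the later visit will be used in the analysis".

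**The concern.** Table 1 uses two offsets between protocol weeks and weeks on drug. Visit 10, protocol Week 64, becomes Week 60 (offset 4), while protocol Week 72 becomes Week 64 (offset 8). Only one can be right for a single first-dose date. With dosing at protocol Week 8 it is 8.

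These windows drive the by-visit summaries of laboratory tests, vital signs, ECG, PD, PK, RWS, TUG, dynamometry, MFM, spirometry, 6-MWT and PGIC. A wrong offset does two things:

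- It mislabels time on drug, so the one-year visit is reported as Week 56.
- It leaves the cut-points badly placed relative to the real visit days. Combined with the later-visit rule, one visit's record can then replace another's.

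In a descriptive study of 14 subjects, one or two displaced records change a visit summary.

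**Working it through.** **Formulas.** Weeks after first dose = protocol week − 8. Study day = 7 × (protocol week − 8) + 1, from the SAP 2.3.2 definition. (Table 1 itself lists scheduled days as 7 × week, a one-day difference in convention only.)

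**Reproducing the plan's figures.** An offset of 4 gives 24 − 4 = 20, 36 − 4 = 32, 48 − 4 = 44, 60 − 4 = 56 and 64 − 4 = 60. That matches the table, but it would put first dose at protocol Week 4. All twelve extension rows use 8 (72 − 64 = 8, through 276 − 268 = 8).

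**Correct dating, Visit 4 on schedule.**

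| Visit | Protocol week | Weeks after first dose | SAP row | Nominal day (permitted) | Intended SAP window | Permitted days outside it |
|---|---|---|---|---|---|---|
| 6 | 24 ± 2 | 16 | 20 | 113 (99–127) | 99–182 | 0 of 29 |
| 7 | 36 ± 2 | 28 | 32 | 197 (183–211) | 183–266 | 0 of 29 |
| 8 | 48 ± 2 | 40 | 44 | 281 (267–295) | 267–350 | 0 of 29 |
| 9 | 60 ± 4 | 52 | 56 | 365 (337–393) | 351–406 | 14 of 57 |
| 10 | 64 ± 2 | 56 | 60 | 393 (379–407) | 407 on | 28 of 29 |

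Each row is 4 weeks (28 days) late. Visits 6 to 8 have no slack on the early side: the first permitted day is the first day of the window.

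**Visit 9.** On Days 337–350 it falls in the Week 44 window, which already holds Visit 8. The later-visit rule keeps Visit 9, drops Visit 8 and leaves Week 56 without a Visit 9 record. The count is 21 of 57 days if Visit 4 was a week late and 7 of 57 if a week early. The documents do not give the spread of visit dates, so the following are assumptions (normal weights by day, truncated at ± 28 days):

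| Assumed spread of Visit 9 | Share on or before Day 350 | Of 14 subjects |
|---|---|---|
| SD 7 days | 1.9% | 0.3 |
| SD 10 days | 7.2% | 1.0 |
| SD 14 days | 13.5% | 1.9 |
| Uniform | 24.6% | 3.4 |

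**Visits 6 to 8 when Visit 4 varies by ± 7 days.** The share slipping into the preceding window is 1.6% for each visit (Visit 4 SD 3.5 days, visit SD 7), 3.5% (SD 3.5 and 14) or 6.4% (both uniform).

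**Visit 10.** Days 379–406 fall in the Week 56 window; only Day 407 reaches the end-of-study row. With Visit 4 a week early, 21 of 29 days fall in Week 56; a week late, 29 of 29. A safety follow-up 7 ± 3 days after a last dose on Day 365 (Days 369–375) lands there too.

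**Does the 12-week spacing text explain the SAP rows?** Counting from Visit 5 at protocol Week 12, 14 or 16 gives 16/28/40/52, 18/30/42/54 or 20/32/44/56 weeks after first dose. Only the last matches. It implies protocol Weeks 28, 40, 52 and 64, which puts Visits 6 to 8 outside their ± 2-week tolerances and Visit 9 on the week the same sentence gives to Visit 10.

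**Corrected cut-points.** The existing limits are midpoints of the scheduled days, for example (56 + 140)/2 = 98 and (308 + 392)/2 = 350. Applied to Days 56, 112, 196, 280 and 364, the same rule gives 84, 154, 238 and 322. Day 406 remains the midpoint of Visit 9 and protocol Week 72: (364 + 448)/2. With these limits no permitted Visit 6 to 9 day is misfiled, even if Visit 4 varies by ± 1 week.

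**The case against.** - **Mostly a labelling fault.** On-schedule Visits 6 to 9 reach their intended rows, exposure is computed from dose dates (SAP 3.2.1), and all data are listed. This stands and limits the weight of the point.
- **Visit 10 may be assigned by name.** The end-of-study row names a protocol visit, and it overlaps the Week 72 row beyond Day 406, so day alone cannot separate the two. On that reading the Visit 10 misfiling disappears. But the SAP says the windows assign the data and prints a window for this row. The 28-day error and the Visit 9 problem remain on either reading.
- **Few measures are repeated at Visit 10.** This largely stands. SAP section 3.4 ends RWS, TUG, dynamometry, PGIC, MFM, spirometry and 6-MWT at Week 60, and protocol Table 2, footnote n, lists PD blood for Visits 4 to 9 and early termination only. ECG is stated for Visits 4 to 10 (SAP 3.2.4.3). Vital signs and weight appear to be repeated, but the table layout is broken in the text available. The effect would be wider only if the tie rule were programmed to drop a whole visit rather than a parameter.
- **The spreads are assumed.** True, hence the range. SAP section 5 reports visits missed because of COVID-19, and nothing shows that visits ran early.
- **The new limits tolerate less lateness.** Visit 7, for instance, now stays in its window up to 69 days late (266 − 197) and would stay up to 41 (238 − 197). That is a real trade-off, but today's window allows only 14 days on the early side; the new one is nearly symmetric.
- **The protocol's own spacing text gives the SAP rows for an 8-week Visit 5.** It does, but only by breaking the Table 2 visit weeks. It is a reason to reconcile the protocol as well.

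**Conclusion.** The point holds. Given first dose at protocol Week 8, all five rows for Visits 6 to 10 are 28 days late, and Table 1 contradicts its own extension rows.

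The label error is certain. The misfiling of Visit 9 needs a visit at least 15 days early when Visit 4 is on time: 14 of 57 permitted days, or about 0.3 to 3.4 of 14 subjects under the assumed spreads. The misfiling of Visit 10 follows from assignment by day and covers 28 of 29 permitted days, including the nominal one. It concerns only subjects who do not roll over (0 to 14, number not given), and chiefly ECG, which is part of the primary safety endpoint.

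Adverse-event counts, change-to-end-of-treatment summaries (SAP 2.3.3), MRI, FSHD-RODS and FSHD-HI (by protocol visit, SAP section 5) are unaffected. The table should be corrected, but no inferential conclusion is at risk.

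**What to change.** In SAP Table 1, re-date the five rows: Visit 6 to Week 16 (Day 112), Visit 7 to Week 28 (Day 196), Visit 8 to Week 40 (Day 280), Visit 9 to Week 52 (Day 364) and Visit 10 to Week 56 (Day 392). Set the limits at Days 84, 154, 238 and 322, with 406 as the upper limit for Visit 9.

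Do not separate Visits 9 and 10 by day, because their permitted ranges share Days 379–393 (15 days). Assign Visit 10 and any off-drug follow-up to end of study by visit label or on/off-drug status, and state that they never replace an on-treatment record. This also removes the overlap with the Week 72 row. Bring the sentence below the table that refers to Weeks 56 and 60 into line. Because SAP section 5 reports missed visits, list any Visit 6 to 8 that was 42 to 69 days late before the re-run, since those would change window.

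Reconcile the 12-week spacing in protocol section 3.1.3 with the visit weeks in protocol Table 2.

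The cost is a table edit, one added sentence, a protocol wording correction and a re-run of by-visit outputs. No new data are needed.
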